### ***7.3.5.3.1 Total alkaline phosphatase response rate***

Old text:

Total ALP response is defined with respect to each applicable baseline, as a  $\geq 30\%$  reduction of the blood total-ALP level compared to the baseline value.

New text:

Total ALP response is defined with respect to each applicable baseline, as a  $\geq 30\%$  reduction of the blood total-ALP level compared to the baseline value, confirmed by a second consecutive ALP value 4 or more weeks later but within 9 weeks, among evaluable subjects.

### ***7.3.5.3.2 Time to total alkaline phosphatase progression***

Old text:

Total ALP progression is defined with respect to each applicable baseline, as a  $\geq 25\%$  ~~increase above the applicable nadir (lowest respective baseline or post-baseline) value.~~

New text:

$\geq 25\%$  increase from baseline value, at least 12 weeks from baseline in subjects with no ALP decline from baseline; or  $\geq 25\%$  increase above the nadir value, which is confirmed by a second consecutive value obtained 3 or more weeks later but within 9 weeks in subjects with an initial ALP decline from the baseline.

### ***7.3.5.4.1 Prostate specific antigen response rate***

Old text:

Prostate specific antigen response is defined in each evaluable subject with respect to each applicable baseline as a  $\geq 30\%$  reduction of the blood PSA level, compared to the baseline

value, confirmed by a second subsequent PSA value with a  $\geq 30\%$  reduction from the applicable baseline approximately 4 or more weeks later.

New text:

Prostate specific antigen response is defined in each evaluable subject with respect to each applicable baseline as a  $\geq 30\%$  reduction of the blood PSA level, compared to the baseline value, confirmed by a second subsequent PSA value with a  $\geq 30\%$  reduction from the applicable baseline approximately 4 or more weeks later but within 9 weeks.

#### **7.3.5.4.2 Time to prostate specific antigen progression**

Old text:

Prostate specific antigen progression is defined with respect to each applicable baseline, as a  $\geq 25\%$  increase ~~above the applicable nadir (lowest baseline or post-baseline) value, and an increase in absolute value of  $\geq 2$  ng/mL above the nadir.~~

New text:

Prostate specific antigen progression is defined with respect to each applicable baseline, as a  $\geq 25\%$  increase from baseline value and an increase in absolute value of  $\geq 2$  ng/mL, at least 12 weeks from the applicable baseline in subjects with no PSA decline from baseline; or  $\geq 25\%$  increase and an absolute increase of  $\geq 2$  ng/mL above the nadir value, which is confirmed by a second consecutive value obtained 3 or more weeks later but within 9 weeks in subjects with an initial PSA decline from the baseline.

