- b Once a separate, extended safety follow-up protocol, for the inclusion of subjects who received radium-223 dichloride in the course of Bayer sponsored clinical studies, has been implemented, the study subjects surviving after the end of the 2 years of active follow-up will be transitioned to this separate, extended safety follow-up protocol and the current study will be terminated at the time the last study subject is transitioned.
- c The maximum period for rescreening screen failed subjects is 35 days (14 days screening + 7-day window + 14 days for rescreening) from signing the ICF to randomization. Rescreening of a subject requires prior approval of the Bayer-designated medical representative (see Section 5.1). Eligibility should be confirmed within 14 ± 7 days of randomization.
- d The subject should return to the clinic in advance of the scheduled dose visit such that results of the laboratory assessment are available within 72 hours prior to dosing (each dose period is 28 ± 7 days after the prior dose of radium-223 dichloride).
- e Subjects who can no longer travel to the clinical site or who receive further anticancer therapy will only be followed up by telephone (active follow-up without clinic visits). Symptomatic skeletal events will not be collected over the phone.
- f The study record or subject's clinical record must clearly show that informed consent was obtained prior to any other study procedures being performed. Eligibility should be confirmed during the screening period and reconfirmed prior to dosing at Dose 1, Day 1.
- g Reconfirmation of eligibility and registration in the IVRS / IWRS: hematology results obtained within 72 hours of Dose 1, Day 1 should be reviewed and it should be confirmed that the values are still within the treatment ranges (absolute neutrophil count ≥ 1.5 x 10^9/L, platelet count ≥ 100 x 10^9/L, and hemoglobin ≥ 9.0 g/dL).

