#### ***Section 7.1.2.7.1. Active Follow-up with clinic visits:***

Old text:

The subject should return to the clinic every 12 weeks ( $\pm$  14 days) following the EOT visit until the subject experiences a symptomatic skeletal event or until the primary efficacy analysis matures, whichever occurs first; ~~provided that active follow-up will not last less than 2 years or more than 7 years following the subject's last study treatment.~~

In addition to the visits at Weeks 36 and 48, the subjects in Treatment Arms A and B will receive telephone contacts at Weeks 28, 32, 40, and 44 to assess for possible SSE risks and will continue PRO data collection. Pain data, 24-hour analgesic use, BPI and NCCN-FACT FPSI-17 questionnaires will also be collected as detailed below.

New text:

The subject should return to the clinic every 12 weeks ( $\pm$  14 days) following the EOT visit until the subject experiences a symptomatic skeletal event or until the primary efficacy analysis matures, whichever occurs first. Active follow-up will continue for 2 years in this study and not more than 7 years total including the long term follow-up study (if the subject has signed the ICF).

To the extent possible, subjects discontinuing treatment prematurely should nonetheless complete the Week 8, 16, 24, 36, and 48 clinic visits and any applicable tumor assessments scheduled with respect to treatment start. Similarly, subjects in Treatment Arms A and B should receive Week 28, 32, 40, and 44 telephone contacts at the regularly scheduled time with respect to treatment start.

In addition to the visits at Weeks 36 and 48 (from the start of treatment) the subjects in Treatment Arms A and B will receive telephone contacts at Weeks 28, 32, 40, and 44 (from the start of treatment) to assess for possible SSE risks and will continue PRO data collection. Pain data, 24-hour analgesic use, BPI and NCCN-FACT FPSI-17 questionnaires will also be collected as detailed below.

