#### ***Section 7.3.4.4.1 Pain improvement rate***

1st paragraph

Old text:

~~Pain improvement is defined for each baseline in subjects evaluable for pain improvement at that baseline, i.e., subjects entering the study with a WPS of at least 4 and evaluable for analgesic use increase at the respective baseline assessment. Pain improvement with respect to each baseline is defined in each applicable evaluable subject at each applicable post-baseline assessment time point as a 30% and 2-point decrease in WPS over 2 consecutive measurements conducted at least 4 weeks apart, without an increase in analgesic use.~~

New text:

Pain improvement is defined for each baseline in subjects evaluable for pain improvement at that baseline, i.e., subjects entering the study with a WPS of at least 4 at the respective baseline assessment. Pain improvement with respect to each baseline is defined in each applicable evaluable subject at each applicable post-baseline assessment time point as a 30% and 2-point decrease in WPS over 2 consecutive measurements conducted at least 4 weeks apart.

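### The 9-week confirmation limit for PSA and ALP does not fit 12-weekly sampling after end of treatment, so after the 6th dose Arm A can almost never confirm what Arm C can

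*Protocol*

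**What the plan says.** Amendment 3 (Change 6) rewrote four exploratory definitions and gave each a 9-week limit on the confirming value.

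- Section 7.3.5.4.2, PSA progression after an initial decline: a rise above nadir "which is confirmed by a second consecutive value obtained 3 or more weeks later but within 9 weeks in subjects with an initial PSA decline".
- Section 7.3.5.3.2, ALP progression after an initial decline: a rise above nadir "which is confirmed by a second consecutive value obtained 3 or more weeks later but within 9 weeks in subjects with an initial ALP decline".
- Section 7.3.5.3.1, ALP response: "confirmed by a second consecutive ALP value 4 or more weeks later but within 9 weeks, among evaluable subjects".
- Section 7.3.5.4.1, PSA response: the same 9-week limit, with a minimum gap of only approximately 4 weeks.

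On timing, Table 7-1 (footnote d) states that "each dose period is 28 ± 7 days after the prior dose of radium-223 dichloride". After the end-of-treatment (EOT) visit, Section 7.1.2.7.1 says: "The subject should return to the clinic every 12 weeks". Arms A and B have clinic visits at Weeks 36 and 48. Their contacts at Weeks 28, 32, 40 and 44 are by telephone and collect pain, analgesic use and questionnaires, not blood. Arm C has PSA and chemistry (including ALP) at each 4-weekly dosing visit to Week 44.

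Section 7.3.2 defines response and progression endpoints from two baselines, screening and the 6th dose date. The second serves the comparison of Arm A with Arm C.

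**The concern.** A confirmation rule works only if the schedule supplies a second sample inside the permitted interval. Here the limit is 63 days and the follow-up spacing is 84 days. In the weeks after Dose 6, Arm A is on the 12-weekly schedule while Arm C is still sampled every 4 weeks. The same PSA or ALP course could therefore count as a confirmed response, or as a confirmed rise from nadir, in Arm C and not in Arm A. Response rates and times to progression would then partly measure how often blood was drawn.

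**Working it through.** The plan gives no figure for this point, so there is none to reproduce. The check is arithmetic on visit days.

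**Inputs**
- Limit: 9 × 7 = 63 days. Minimum gap: 21 days for progression, 28 days for ALP response.
- Dosing visits every 28 ± 7 days: Dose 6 at Week 20 (day 140); in Arm C, Dose 12 at Week 44 (day 308).
- EOT 30 ± 7 days after the last dose (Section 6.8): day 170 in Arm A, day 338 in Arm C.
- Follow-up every 84 days, ± 14 days in Section 7.1.2.7.1 but ± 7 days in Section 4.1 (both were run). Weeks 36 and 48 are days 252 and 336.
- The second baseline is the last value on or before the 6th injection (Amendment 3, Change 5 rationale), so the first later scheduled sample is EOT in Arm A and Dose 7 in Arm C.

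**Step 1: nominal gaps after the 6th-dose baseline, to Week 48**

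| Arm | Sampling days | Gaps (days) | Within 63 days |
|---|---|---|---|
| A | 170, 252, 336 | 82, 84 | 0 of 2 |
| C | 168, 196, 224, 252, 280, 308, 338 | 28, 28, 28, 28, 28, 30 | 6 of 6 |

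Counted from Dose 1, the figures are 6 of 8 pairs in Arms A and B and 12 of 12 in Arm C.

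**Step 2: do the visit windows rescue Arm A?** Visits are assumed uniform over whole days, because no distribution is given.
- Window applied to the interval: 84 ± 14 gives 70–98 days and 84 ± 7 gives 77–91 days. None is within 63.
- Window around fixed dates: gap = 84 + d2 − d1. With ± 7 the smallest gap is 84 − 14 = 70, so none qualifies. With ± 14 the smallest is 84 − 28 = 56. A gap of 63 or less needs d1 − d2 ≥ 21, which holds for 8 + 7 + … + 1 = 36 of 29 × 29 = 841 combinations (4.3%).
- EOT to Week 36, simulated. With Dose 6 within ± 7 days of day 140, 0.3% qualify (Week 36 ± 7) or 3.4% (± 14). With each dosing interval free to vary from 21 to 35 days and the drift accumulating, 5.4% or 8.8% qualify.

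The range is about 0% to 9%.

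**Step 3: the other progression branch.** With no decline from baseline, progression needs a sufficient rise at least 12 weeks from baseline and no confirming value. Week 36 is 36 − 20 = 16 weeks after the 6th-dose baseline, so Arm A can meet this branch at a single visit.

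**Step 4: the 4-week minimum (minor).** ALP response requires at least 4 weeks, and pain improvement requires a decrease "over 2 consecutive measurements conducted at least 4 weeks apart". Of the permitted gaps of 21 to 35 days, 7 of 15 (46.7%) are under 28 days if all are equally likely. If 50% of visits fall exactly on day 28 and the rest are spread evenly, the share is 0.5 × 0.5 = 25%. With 75% it is 12.5%, and with all on day 28 it is 0%.

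**Step 5: after the fix.** Two 12-weekly visits with ± 14-day windows are at most 84 + 28 = 112 days (16 weeks) apart. On a common grid near Weeks 24, 36 and 48, the gaps are 82 and 84 days in Arm A, and 252 − 168 = 84 and 338 − 252 = 86 days in Arm C. Both arms then have 2 of 2 nominal pairs.

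**The case against.** Several points on the other side stand.

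- **Exploratory endpoints.** PSA and ALP sit in Section 7.3.5. Hypothesis tests are confined to the primary endpoint, OS, time to first SSE, time to radiological progression and rPFS. Section 8.4.2.2 sets the 6th-dose reference date for secondary analyses. For PSA and ALP the second baseline comes from Section 7.3.2, which leaves its details to the SAP.
- **Limited period.** All arms are sampled 4-weekly until about Week 24, and Arm C also moves to 12-weekly visits after about Week 48.
- **Deliberate limit.** The stated reason for Change 6 is consistency across the radium-223 programme, so dropping the limit has a cost.
- **Text available.** Only part of the protocol was available. Amendment 4 touched the schedule sections through a separate tracked-changes document, although its listed changes concern neither these definitions nor sampling frequency.

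Three stronger readings are tempting and are not supported. A reader might infer that PSA and ALP progression in general will be found mainly in Arm C. The no-decline branch needs no confirmation, and the documents do not say what share of progressions falls in each branch. A reader might infer that confirmation in Arm A is impossible, but a few pairs can fall within 63 days, as can unscheduled samples. A reader might also infer that the 4-week minimum biases the pain endpoints between arms or loses true responders. Pain is collected every 4 weeks to Week 48 in all arms, and a sustained change can qualify at a later pair. Even at 7 of 15 with independent gaps, a change spanning three pairs is missed in (7/15)³ = 10% of cases, and one spanning five pairs in 2%.

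**Conclusion.** The concern holds in limited form. Applied as written, the 9-week limit leaves Arm A with 0 of 2 nominal confirmable pairs between the 6th-dose baseline and Week 48, against 6 of 6 in Arm C. Visit windows raise the Arm A chance to no more than about 9% per pair on the assumptions used. PSA and ALP response, and progression from nadir, are therefore not comparable between these arms from about Week 24 to Week 48. The primary analysis and the tested secondary endpoints stand.

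The result assumes the scheduled visits only, uniform timing within windows, and no dose delay beyond ± 7 days per interval. A longer delay could bring EOT within 63 days of Week 36: 82 − 63 = 19 days of accumulated delay would be enough if Week 36 stays tied to treatment start. It would not help if follow-up runs 12-weekly from EOT.

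The 4-week minimum is a minor wording point that affects all arms alike. It excludes 0% to 47% of permitted pairs, depending on visit timing that the documents do not give.

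**What to change.** 1. For PSA and ALP, define confirmation as the next scheduled value, at least 3 weeks later for progression and about 4 weeks later for response, with a ceiling of about 16 weeks (112 days). A 14-week ceiling (98 days) is enough only if the ± 14 days applies to the interval itself.
2. For Arm A versus Arm C after the 6th dose, use only sampling points scheduled in both arms (about Weeks 24, 36 and 48), and read consecutive as consecutive on that grid.
3. For ALP response and the pain endpoints, let the 4-week minimum allow for the visit window, as PSA response already does by making its minimum approximate.

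The cost is protocol and SAP wording applied to data already collected. Confirmation becomes coarser and later, Arm C's interim values go unused in that one comparison, and the definitions depart from the programme-wide ones. Keeping the 9-week rule as a sensitivity analysis preserves that link.

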### **Change 7**

#### **7.3.4.3 Radiological progression endpoints**

Deleted text:

~~The central reviewer will determine the applicable baseline values for and assess radiological progression with respect to each applicable baseline.~~

## **13.4 Amendment 4**

### **Description of the amendment**

Amendment 4 is an amendment to the integrated protocol version 4.0 dated 16 MAY 2017.

Changes to the protocol include:

- Addition that radium-223 dichloride should not be given with abiraterone plus prednisone/prednisolone.
- New request that bone fractures and bone associated events (e.g., osteoporosis) need to be reported as (S)AEs, including during long-term follow-up, regardless of causality to study treatment.
- Based on the available data on radium-223 dichloride, initiation of BHAs during the follow-up periods, including bisphosphonates or denosumab, should be considered taking into consideration applicable guidelines.

- Updated the study GCL and study medical expert names.
- Minor clarifications

### 13.4.1 Overview of changes

#### 13.4.1.1 Change 1:

Addition that radium-223 dichloride should not be given with abiraterone plus prednisone/prednisolone.

Sections affected include:

- Synopsis - Background treatment / concomitant medications / prohibited therapies
- 6.9.2 Concomitant medication
- 7.1.1 Tabulated overview, Schedule of procedures

*Rationale:* The ERA 223 study, a phase III randomized trial in prostate cancer patients examining radium-223 dichloride versus placebo in combination with abiraterone and prednisone (study number 15396, NCT02043678) was unblinded based on the Independent Data Monitoring Committee (IDMC) recommendation following an ad hoc independent analysis where more treatment emergent fractures, SSE-FS, and total deaths events were observed in the active treatment arm compared with the placebo arm. Based on the available data, the benefit-risk of radium-223 dichloride in combination with abiraterone acetate plus prednisone/prednisolone in mCRPC is considered unfavorable.

#### 13.4.1.2 Change 2:

Bone fractures and bone associated events (e.g., osteoporosis) need to be reported as (S)AEs, including during long-term follow-up, regardless of causality to study treatment.

Sections affected include:

- Synopsis - Methodology
- 4.1 Design overview
- 6.8 Post-study therapy
- 7.1.1 Tabulated overview
- 7.1.2.7.1 Active follow-up with clinic visits
- 7.1.2.7.2 Active follow-up without scheduled clinic visits
- 7.1.2.8.1 End of active follow-up with clinic visits
- 7.1.2.8.2 End of active follow-up without scheduled clinic visits

- 7.1.2.9 Long-term follow-up to 7 years following last dose
- 7.1.2.9.1 Long-term follow-up (via telephone follow-up)
- 7.1.2.9.2 End of long-term follow-up
- 7.5.1.3 Assessments and documentation of adverse events
- 7.5.1.4 Reporting of serious adverse events
- 10 Premature termination of the study

*Rationale:* The ERA 223 study, a phase III randomized trial in prostate cancer patients examining radium-223 dichloride versus placebo in combination with abiraterone and prednisone (study number 15396, NCT02043678) was unblinded based on the IDMC recommendation following an ad hoc independent analysis where more treatment emergent fractures, SSE-FS, and total deaths events were observed in the active treatment arm compared with the placebo arm. Based on these data European Health Authorities requested that all bone fractures and bone associated events (e.g., osteoporosis) occurring during study and in the follow-up period should be documented regardless of causality to study treatment.

#### **13.4.1.3 Change 3:**

The option of starting a BHA during the follow-up periods, including bisphosphonates or denosumab, should be considered taking into consideration applicable guidelines.

Sections affected include:

- Synopsis - Methodology
- 6.9.2 Concomitant medication

*Rationale:* The ERA 223 study, a phase III randomized trial in prostate cancer patients examining radium-223 dichloride versus placebo in combination with abiraterone and prednisone (study number 15396, NCT02043678) was unblinded based on the IDMC recommendation following an ad hoc independent analysis where more treatment emergent fractures, SSE-FS, and total deaths events were observed in the active treatment arm compared with the placebo arm. Based on the available data on radium-223 dichloride, the option of starting a BHA including bisphosphonates or denosumab should be considered, taking into consideration applicable guidelines.

#### **13.4.1.4 Change 4:**

Updated the study GCL and Study Medical Expert names.

Sections affected:

- Title page
- Signature of the sponsor's medically responsible person

- 3 Investigators and other study personnel

*Rationale:* Change reflects the current medical expert and protocol signatory.

#### **13.4.1.5 Minor clarifications:**

- Added the definition for Independent Data Monitoring Committee (IDMC) and bone health agent (BHA) in the list of abbreviations and in the text where appropriate.
- For Word-related technical reasons, numbered footnotes have been replaced with a summary of changes at the start of each amended section.

#### **13.4.2 Changes to the protocol text**

Changes to the protocol text are provided in a separate tracked changes document.

## 14. Appendices

### 14.1 Response Evaluation Criteria in Solid Tumors, version 1.1

*Section modified by Amendment 2 (Section 13.2).*

Soft tissue response and progression will be evaluated in this study using a modified version of the modified RECIST guidelines version 1.1.

Modification to RECIST:

- Only lymph nodes with short axis  $\geq 1.5$  cm can be selected as target lesions.
- Disease progression at first assessment needs to be confirmed by a second scan 6 or more weeks later as required per the PCWG2 guidance.(1) In case of unequivocal progression, a confirmatory scan is not mandatory and it will be performed at the investigator's discretion.
- Bone lesions will not be recorded as non-target lesions or assessed per modified RECIST. Radiological progression of bone lesions will be determined according to PCWG2 criteria based on whole body technetium-99 bone scans.

**Measurable Disease:** Note: Subjects are excluded if they have visceral metastases as assessed by abdominal and pelvic MRI / CT scan or chest X-ray.

**Malignant lymph nodes:** To be considered pathologically enlarged and measurable, a lymph node must be  $\geq 1.5$  cm in short axis when assessed by CT scan. At baseline and in follow-up, only the short axis will be measured and followed.

Malignant lymph nodes situated in a previously irradiated area are not considered measurable unless there has been demonstrated progression in the lesion.

**Non-Measurable Disease:** All other lesions (or sites of disease), including small lesions (pathological lymph nodes with short axis  $\geq 1$  cm to  $< 1.5$  cm) are considered non-measurable disease. Leptomeningeal disease, ascites, pleural / pericardial effusions, and lymphangitic involvement of skin or lung are all non-measurable.

**Target Lesions:** All measurable lesions up to a maximum of 5 lesions in total, representative of all involved regions should be identified as target lesions and be recorded and measured at baseline. These 5 lesions should be selected on the basis of their size (lesions with the longest short axis), and should be suitable for reproducible repeated measurements. A sum of nodal short axes of target lesions will be calculated and reported as the baseline sum diameters. The baseline sum diameters will be used as reference to further characterize any objective tumor regression of the measurable dimension of the disease. If there are

> 5 measurable lesions, those not selected as target lesions will be considered together with non-measurable disease as non-target lesions.

**Non-target Lesions:** All non-measurable lesions (or sites of disease) plus any measurable lesions over and above the 5 listed as target lesions. Measurements are not required but these lesions should be noted at baseline and should be followed as “present,” “absent,” or in rare cases “unequivocal progression.”

